# 6 Study Methods

#### 6.1 General Study Design and Plan

The IPCAS trial is an open-label, two-level cluster randomised trial of patients clustered within general practices, with randomisation occurring at the level of the general practice.

General practices are randomised in a ratio of 1:1 to the control or experimental group. General practices in the control arm offer standard care to their patients. General practices in the experimental arm offer a novel model of care to their patients. Once all invitation letters and reminders are sent out to patients in a general practice, the general practice can be randomised.

Randomisations are performed using a stratified, random permuted block design. The stratification factor is general practice list size, split into two levels based on the approximate median general practice list size for the geographic areas likely to be included in the trial. The two strata levels are:

- i) Strata 1: General practice list size less than 10,500 patients;
- ii) Strata 2: General practice list size equal to or greater than 10,500 patients.

Random permuted blocks are used in order to maintain close balance in the allocation of the two treatment groups within each strata, and to minimise opportunities for selection bias. The exact block sizes used to produce the randomisation lists is documented separately by the statistician in order to help maintain blinding.

The sequence of key study points is summarised in the following flow chart.

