# 7 Sample Size

With 23 clusters per arm and an average of 20 patients per cluster, assuming an intra-class correlation of 0.03, a typical coefficient of variation of the cluster size of 0.65 (Campbell, 2014), and 2.5% significance (adjusted to 2.5% because of the use of two co-primary outcomes), we would be able to detect an effect size of 0.33 with at least 90% power on the co-primary outcomes (emotion and handicap sub-scales of the Stroke Impact Scale (SIS v3.0)). The sample size calculation has been inflated to allow for a rate of 20% loss to follow-up for patients within clusters. Loss to follow-up of entire clusters is not anticipated.

The conservative estimate of 20 patients per practice is drawn from the trials pilot data (unpublished) and the research groups experiences of running previous trials in this population (Fletcher K, 2010; Fletcher K, 2010; O'Brien C, 2013). A typical practice with a list size of between 7,000 to 10,000 will have approximately 100 - 150 patients on the stroke register (Progress in improving stroke care, 2010). We anticipate that the electronic search applying the exclusion criteria will eliminate around 40% of these (based on the pilot study) leaving 60 – 90 eligible patients per practice, of which about 30% will agree to take part (18 – 27 per practice). This will yield between 16 – 24 participants per practice.

The IPCAS trial was powered based upon the two co-primary outcomes (SIS emotional and handicap domains). It is important to be aware that the trial was not powered based on any secondary or exploratory end-points, and this should be considered in particular when interpreting any resulting p-values.

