# 8.3 Covariates and Subgroups

As the randomisation for the IPCAS trial is stratified by general practice list size (Strata 1: General practice list size less than 10,500 patients; Strata 2: General practice list size equal to or greater than 10,500 patients). There is an *a priori* hypothesis that smaller practices can deliver the intervention more successfully due to more personal care, therefore general practice list size will be adjusted for in the secondary analyses using the same category levels as used in the randomisation. This will be included as a cluster-level fixed effect in the mixed effect models for the analyses of the two coprimary end-points.

Various subject-level covariates are considered as important baseline covariates or clinically significant in this study. These subject-level and cluster-level covariates will be included as subject-level or cluster-level fixed effects in the mixed effects model for the analyses of the two co-primary end-points, and in the mixed effect models of secondary end-points where deemed appropriate:

- Baseline categorical variable gender (male/female).
- Age at baseline in the following categories: 20-64, 65-74, 75-84, 85+ years.
- Time since last stoke at baseline in the following categories: 0-6months, 6 months-1year, 1-2 years, 2-5 years, 5-10years, 10 years +.
- Deprivation score (subject and practice).

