Each data point will be assumed to have an error term that is identically and independently normally distributed with constant variance. These assumptions will be checked using histograms and box plots to look at the distributional form of the primary outcome SIS scores. All assumptions for the linear mixed effects models will be assessed by viewing plots of the residual values and QQ plots. If any of the assumptions of the linear mixed model are violated then the dependent variable, SIS score, may be transformed to normality or if this fails to correct the distributional assumptions, non-Gaussian or semi/non-parametric methods for analysis will be used.

 $Y_{ijk} = \beta_0 X_{0ij} + \beta_1 X_{1ij6} + \beta_2 X_{1ij12} + u_j + \varepsilon_{ijk}$ 

The analysis population for the primary outcome will be all patients with 12-month outcome measure as the mixed effects model assumes missing at random (MAR).

For missing data analysis the following model will be fitted if there is a cluster effect:

Yijk = continuous outcome SIS score (emotion/ handicap domain)

*i* = individual patient

j = cluster/ practice

*k* = 6 month and 12 follow-up scores

 $X_1$  = dummy variable for the intervention treatment group.

X0 = baseline covariates (baseline score, gender, cluster size, time since last stroke at consent)

 $\beta_0$  = intercept which represents the average baseline SIS score for person *i* 

 $\beta_1$  = difference in score between intervention and control groups at 6 months

 $\beta_2$  = difference in score between intervention and control groups at 12 months (primary)

 $u_i \sim N_1(0, \sigma_b^2)$  is the cluster-level random practice effect

$$\begin{pmatrix} Y_{ij0} \\ Y_{ij6} \\ Y_{ij12} \end{pmatrix} \sim MuN \begin{pmatrix} \beta_0 \\ \beta_0 + \beta_1 + X_{ij6} \\ \beta_0 + \beta_2 + X_{ij12} \end{pmatrix}$$

$$\epsilon_{ijk} \sim MuN \begin{pmatrix} 0 \\ 0, \Sigma_0 \\ 0 \end{pmatrix}$$
 is the residual error, and  $\Sigma_0$  initially has an AR1 structure.

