# 11 Missing Data

The primary analysis will be the ITT participants who are in the primary analysis population. Linear mixed effects models will be used to analyse the co-primary end-points that are repeated measured. One key benefit of mixed effect models is that this type of model can include data from incomplete cases, so missing data does not necessarily preclude a subject's data from the analysis. In this instance, missing data will be dealt with using a missing at random (MAR) assumption on the analysis population. The outcome variable will include baseline, 6months and 12months outcomes. The mixed effect model will have participant id as a random effect (i.e. random baseline) and the fixed factors will be time, included as a factor variable, and treatment indicator. To help the MAR assumption the residuals of the model will be assumed to have autocorrelation (if the data allow an unstructured correlation structure stratified by treatment indicator). Additional baseline covariates will be included in the model that are potential confounders.

If there is a large amount of missing outcome data from the questionnaires, we will do a sensitivity analysis missing outcome data for the primary analysis as described in White et al. (2011) and Sullivan *et al* (2018). For each questionnaire, where guidelines exist for missing data, they will be followed (see Section 11.1).

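### The SAP's repeated-measures model fixes each practice's effect across visits, so its 12-month standard error is too small if practice effects change after baseline

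*SAP*

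**What the plan says.** SAP 10.1 gives two clustered models for each co-primary score. The first uses the 12-month score alone, with baseline score among the covariates and a random effect for practice. The second, introduced for the missing-data analysis and fitted only if a cluster effect is present, has a visit index k. Its single practice term u_j "is the cluster-level random practice effect", with one scalar variance and no visit index. The residuals start from an AR1 structure. The coefficient beta_2, the 12-month treatment difference, is labelled primary.

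The SAP is inconsistent about baseline in this second model. The key defines k as the 6- and 12-month scores and puts the baseline score among the covariates. The displayed distribution, however, stacks baseline, 6-month and 12-month scores with a common baseline mean. SAP 11 agrees with the display: "The outcome variable will include baseline, 6months and 12months outcomes". SAP 11 names only a participant random effect and no practice effect, and allows an unstructured correlation if the data permit.

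Neither document plans a practice-by-visit effect. SAP 8.3 states a prior hypothesis that "smaller practices can deliver the intervention more successfully due to more personal care".

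**The concern.** A practice effect with no visit index assumes that a practice sitting above or below the average before randomisation sits equally far above or below it at 12 months. When baseline is part of the outcome, the model uses each practice's baseline deviation to remove its 12-month deviation, and so treats most between-practice variation as accounted for.

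That assumption is open to doubt here. Practices deliver the intervention after baseline, and the SAP itself expects delivery to differ between practices. The list-size adjustment in SAP 8.3 is a main effect that does not vary by visit, so it would not absorb divergence after baseline. If practice effects do drift, the 97.5% interval for beta_2 claims more precision than a practice-randomised comparison has. The analysis meant to support the primary result under missing data would then reject too often.

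**Working it through.** **Inputs.** From SAP 7: "With 23 clusters per arm and an average of 20 patients per cluster", 20% loss (20 × 0.8 = 16 analysed), "intra-class correlation of 0.03", "a typical coefficient of variation of the cluster size of 0.65", and alpha 0.025 per outcome, taken as two-sided to match the 97.5% intervals. From SAP 6.1: "General practices are randomised in a ratio of 1:1". Neither document gives the within-patient correlation r or the between-visit correlation of practice effects (call it ρ), so both are varied as assumptions.

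**The plan's own figure.** Design effect = 1 + ((1 + CV²)m − 1) × ICC.
- m = 16: 1 + (1.4225 × 16 − 1) × 0.03 = 1.653. Effective n per arm = 23 × 16 / 1.653 = 222.7. Power = Φ(0.33 × √(222.7/2) − 2.241) = 89.3%.
- m = 20: design effect 1.824, power 92.9%.

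The stated power of at least 90% is reproduced to within a point. The inputs are therefore a fair basis for what follows, which uses equal practices of 16, complete data and total variance 1.

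**How much practice variance remains (ρ = 1, AR1 patients).** The patient part of a practice mean has variance 0.97/16 = 0.060625. With a common baseline mean, Var(beta_2) = (2/23) × [B₁₂,₁₂ − B₀,₁₂²/B₀₀], where B is the covariance of practice means.
- r = 0.7 (baseline to 12 months, 0.49). With u_j: B₀₀ = B₁₂,₁₂ = 0.090625 and B₀,₁₂ = 0.03 + 0.49 × 0.060625 = 0.059706, so Var = 0.00446. Without u_j: (2/23) × 0.060625 × (1 − 0.49²) = 0.00401. Practice variance adds 0.00045, against the full 2 × 0.03/23 = 0.00261. Share left: 17%.
- r = 0.5: 0.00592 − 0.00494 = 0.00098. Share left: 38%.

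So 62-83% drops out. In an unconstrained change-from-baseline contrast all of it drops out: the SE is 0.0889 (r = 0.5) or 0.0733 (r = 0.7) whether the practice variance is 0 or 0.03. With only 6 and 12 months as outcomes and baseline as a covariate, 100% is left.

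**Effect on the SE of beta_2, baseline as an outcome.** The one-u_j model takes its large-sample maximum-likelihood values. Its SE is compared with the actual (sandwich) SE when practice effects correlate at ρ. Error rate = 2 × [1 − Φ(2.241 × ratio)].

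| Fitted / true patient covariance | r | ρ = 1 | ρ = 0.8 | ρ = 0.5 |
|---|---|---|---|---|
| AR1 / AR1 | 0.6 | 1.00 (2.5%) | 0.95 (3.3%) | 0.89 (4.7%) |
| AR1 / AR1 | 0.7 | 1.00 (2.5%) | 0.94 (3.6%) | 0.86 (5.3%) |
| Unstructured / exchangeable | 0.6 | 1.00 (2.5%) | 0.91 (4.1%) | 0.82 (6.5%) |
| Unstructured / exchangeable | 0.7 | 1.00 (2.5%) | 0.89 (4.7%) | 0.78 (8.1%) |
| AR1 / exchangeable (misfit) | 0.6 | 1.19 (0.8%) | 1.10 (1.4%) | 1.00 (2.5%) |

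Entries are model SE / actual SE, with the error rate at nominal 2.5%. At r = 0.5 with AR1 fitted and true, the error rates are 3.2% (ρ = 0.8) and 4.3% (ρ = 0.5).

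**Effect with baseline as a covariate only.** Nothing cancels against baseline, but under AR1 truth the SE is still about 6-13% too small for ρ from 0.8 to 0. Not all of that is drift: at r = 0.7 the ratio is already 0.92 at ρ = 1.

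**The 12-month model.** Its model SE equals the actual SE in every case (for example 0.0720 for both at AR1, r = 0.7, ρ = 0.8).

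**With a practice-by-visit effect** (AR1, r = 0.7): SE 0.0715 against an actual 0.0716 at ρ = 0.8, and 0.0772 against 0.0779 at ρ = 0.5. The one-u_j model reports 0.0670 and 0.0672.

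**The case against.** The strongest reply is that the damage depends on quantities the documents do not give, in a model with a limited role. Much of this stands.

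- Neither document gives ρ. At ρ = 1 the model is correct. SAP 8.3 concerns how well smaller practices deliver the intervention, so it speaks to the intervention arm only. It makes drift plausible but does not show that practice effects must change, and the calculation imposes drift in both arms.
- The key to the model can be read as keeping baseline out of the outcome, and then there is no cancellation against baseline.
- Under the AR1 structure that SAP 10.1 starts from, an exchangeable truth makes the SE too wide or about right down to ρ = 0.5. This is only partly a defence. AR1 is an initial choice and SAP 11 allows an unstructured form, under which the offset disappears. Two misspecifications that happen to cancel do not make an interval valid.
- SAP 10.1 offers the model for missing data, SAP 12 adds multilevel multiple imputation, and the single-visit 12-month model is sound. Against that, beta_2 carries the primary label, SAP 11 speaks of analysing the co-primary endpoints as repeated measures, and 97.5% intervals are to be reported for the mixed-model coefficients. The limited role is therefore not secure.
- SAP 11 cannot be cited for the same defect, because it names no practice effect at all. It matters here because it makes baseline an outcome and because it conflicts with SAP 10.1.

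**Conclusion.** The concern holds in a conditional form. With baseline as an outcome, the repeated-measures model removes most but not all practice variance from the 12-month effect, and its SE is too small if practice effects change between visits. With ICC 0.03, r = 0.6-0.7 and a correctly specified patient covariance, the shortfall is about 5-11% at ρ = 0.8 and 11-22% at ρ = 0.5, and nil at ρ = 1. These figures also assume equal practices of 16, complete data and a normal reference; small-sample degrees of freedom were not considered.

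A reader might infer that practice differences cancel entirely, that the interval is wrong whatever happens, or that error rates of 8-10% apply to the model as displayed. The documents do not support these readings. Full cancellation needs an unconstrained change contrast. Drift is an assumption. Error rates of that size at moderate drift need an unstructured patient covariance combined with the u_j of SAP 10.1. With AR1 fitted and r = 0.6, the rate is 3.3-5.9% if AR1 is true and 1.4-3.8% if the truth is exchangeable, for ρ from 0.8 to 0.2. Nor is the main 12-month estimate in doubt, provided that the single-visit model is the confirmatory one.

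**What to change.** 1. State in SAP 10.1 whether baseline is an outcome or a covariate in the repeated-measures model, and make the key, the equation and the displayed distribution agree.
2. Reconcile SAP 10.1 with SAP 11, so that one set of random effects, including practice, is specified.
3. Add a practice-by-visit random effect, or correlated visit-specific practice effects, to the repeated-measures model.
4. Name the single-visit 12-month model as the confirmatory analysis, and clarify the primary label on beta_2 accordingly.

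The cost is one extra variance component. With 46 practices it may be estimated near zero, in which case the result reverts to the planned model. Where drift is real the interval widens: in the AR1, r = 0.7 example by about 7% at ρ = 0.8 (0.0715/0.0670) and 15% at ρ = 0.5 (0.0772/0.0672). No further data are needed.

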#### 8.6 Multiple Testing

This study has two co-primary outcomes: (emotion and handicap subscales of the SIS). The Holm-Bonferroni procedure (Holm, 1979) will be used to handle the co-primary endpoints and issue of multiplicity. 97.5% Cls for the two primary outcomes will be reported as a conservative measure.

Confidence intervals for secondary and exploratory outcomes will be reported at the 95% level.

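### SAP Sections 10.1 and 11 give two different covariance models for one repeated-measures analysis, and the unstructured option in Section 11 carries one parameter too many

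*SAP*

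**What the plan says.** SAP Section 10.1 first gives a model for the 12-month score alone, with a practice random effect and baseline score among the covariates. It has no within-patient covariance. The section then gives a second model, introduced for the missing-data analysis, whose displayed outcome vector holds baseline, 6 and 12 months. Practice is its only random effect, and its residual covariance "initially has an AR1 structure". No rule says when AR1 gives way or to what. The 12-month coefficient of this second model is labelled as primary.

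Section 11 describes the repeated-measures analysis again, with all three visits as outcomes. Here, "The mixed effect model will have participant id as a random effect (i.e. random baseline"). The residuals are autocorrelated, with the qualification "if the data allow an unstructured correlation structure stratified by treatment indicator". Section 11 does not mention the practice effect.

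For scale, Section 7 sets "2.5% significance (adjusted to 2.5% because of the use of two co-primary outcomes"), and Section 8.6 says that 97.5% intervals "will be reported as a conservative measure".

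**The concern.** Two covariance models for one analysis leave the analyst to choose after seeing data. Two features make the choice matter.

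- **AR1 alone is rigid.** Over three equally spaced visits it forces the baseline-to-12-month correlation to be the square of the 6-month correlation, and it assumes one SD at all visits. Patient-reported scores often correlate nearly as well over 12 months as over 6. If so, AR1 gives baseline too little weight and the standard error of the 12-month effect is wrong.
- **The unstructured option that is spelled out is redundant.** A participant intercept on top of an unstructured residual is one parameter more than three visits can support. A convergence failure or warning could then be read as the data not allowing it, when the cause is algebra.

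At stake is the width of a 12-month interval, and the test that goes with it, for the co-primary outcomes.

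**Working it through.** **Plan's own figure.** No interval width is stated, so only the power can be reproduced. Inputs from Section 7: "With 23 clusters per arm and an average of 20 patients per cluster", "assuming an intra-class correlation of 0.03", a cluster-size CV of 0.65, and 2.5% significance (taken as two-sided).

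- Design effect = 1 + ((1 + CV²)m − 1) × ICC. For m = 20: 1 + (1.4225 × 20 − 1) × 0.03 = 1.8235. Effective n per arm = 460/1.8235 = 252; power at 0.33 SD = 92.9%.
- For m = 16 (after 20% loss): 1.6528; 368/1.6528 = 223; power = 89.3%.

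This agrees, to within a point after loss, with "effect size of 0.33 with at least 90% power". The calculation uses no between-visit covariance and so does not settle the present point.

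**Redundancy.** Write the participant variance as v and the residual matrix as Σ. The marginal covariance is vJ + Σ, where J is all ones. For any small c, (v − c)J + (Σ + cJ) is the same matrix. Three visits supply 6 variances and covariances; the model uses 1 + 6 = 7 parameters. With separate Σ per arm and a shared intercept there are 13 parameters of rank 12. With a common variance and correlations by arm there are 8 of rank 7. Each is one too many. AR1 plus intercept has 3 parameters of rank 3 and is identifiable. The marginal covariance, and so the treatment effect, is identified throughout.

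**Interval width.** Assumptions: large sample, complete data, common baseline mean, practice effect omitted. Let a be the correlation between adjacent visits and b the baseline-to-12-month correlation, with equal SDs.

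- Unstructured SE is proportional to √(1 − b²).
- The best-fitting AR1 has parameter a and implies a² at 12 months, so its SE is proportional to √(1 − a⁴).
- Ratio = √((1 − a⁴)/(1 − b²)). For exchangeable r this is √(1 + r²). At 0.7: √1.49 = 1.22.

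Ratios to the unstructured interval (unequal-SD cases solved numerically):

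| Assumed truth | AR1 alone | Participant intercept + AR1 |
|---|---|---|
| Exchangeable 0.5 | 1.12 | 1.00 |
| Exchangeable 0.6 | 1.17 | 1.00 |
| Exchangeable 0.7 | 1.22 | 1.00 |
| Exchangeable 0.8 | 1.28 | 1.00 |
| AR1 0.7, equal SDs | 1.00 | 1.00 |
| a = 0.7, b = 0.4 | 0.95 | 0.95 |
| AR1 0.7, SDs 1, 1.1, 1.2 | 0.92 | 0.92 |
| AR1 0.7, SDs 1, 1.2, 1.4 | 0.87 | 0.87 |
| Exchangeable 0.7, SDs 1, 1, 1.25 | 1.07 | 0.90 |
| Exchangeable 0.7, SDs 1, 0.85, 0.7 | 1.51 | 1.30 |

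With an assumed 15% missing at 6 months and 20% at 12, the AR1-alone ratios at exchangeable 0.6 and 0.7 are 1.16 and 1.21.

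**Reported against actual SE.** AR1 alone weights baseline by r² instead of r, so under exchangeability its estimate has true variance proportional to 1 + r⁴ − 2r³. At r = 0.6: √(0.8704/0.6976) = 1.12. At 0.7: √(0.7599/0.5541) = 1.17. With critical value 2.241, null rejection falls from 2.5% to about 1.2% and 0.9%. Simulation with the practice effect included (46 practices of 16, ICC 0.03, 650 null trials per case) gave 1.20 and 1.24. Leaving out the practice effect therefore understates the inflation in these two cases.

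**Two-visit reading.** Section 10.1 also defines its visit index as 6 and 12 months only and lists baseline as a covariate. AR1 then has a single lag and equals compound symmetry, so only unequal SDs matter: ratio ≈ √((s₆² + s₁₂²)/(2s₁₂²)). For SDs 1.2 then 1 this is 1.10; for 1 then 1.2 it is 0.92.

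**The case against.** The strongest reply has four parts.

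- **Section 11 starts from participant intercept plus AR1, not AR1 alone.** An unstructured fit that failed there would fall back to that model, which reproduces every exchangeable equal-SD case exactly. This stands for those cases. It does not stand when SDs change over time (0.87 to 1.30 in the table), and it does not help if the Section 10.1 formula is the one programmed.
- **AR1 is only the initial structure in Section 10.1.** An unstructured residual in that model, which has no participant effect, would be identifiable. So Section 11 is the only route spelled out, not the only one possible. But Section 10.1 gives no criterion for taking the other route.
- **The headline analysis may not be touched.** The 12-month-only model contains no AR1 term. This stands if that model is primary. The SAP does not settle it, because the repeated-measures 12-month coefficient carries the primary label and Section 11 treats the co-primary outcomes as repeated measures.
- **On the two-visit reading the squared-correlation problem vanishes.** This also stands, but the displayed vector and Section 11 both include baseline as an outcome.

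A reader might infer more than this: that the redundancy itself widens the interval, that some percentage is a ceiling, or that any error is on the safe side. None of these holds. The redundancy leaves the effect and its standard error identified. The documents give no correlations or SDs from which a ceiling could be set. Several plausible covariances make the interval too narrow.

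**Conclusion.** The point holds as a defect of specification. Sections 10.1 and 11 describe different covariance models, no switching rule is given, and the unstructured option in Section 11 is over-parameterised by one. The parameter count needs no assumption beyond three visits as outcomes.

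The effect on the interval is conditional. It arises only if AR1 is kept and does not fit, and its direction depends on the true covariance. The sizes rest on assumed correlations and SDs and are illustrations, not predictions for this trial. Harm to the point estimate was not seen: a simulation with about 18% missing-at-random dropout at 12 months showed no material bias from AR1. The matter is worth correcting before analysis, but it is not evidence that the co-primary result would be invalid.

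**What to change.** 1. Reconcile Sections 10.1 and 11 into one repeated-measures model, and state whether baseline is an outcome or a covariate.
2. State whether that model or the 12-month-only model is primary.
3. With three visits as outcomes, specify an unstructured 3 × 3 within-participant residual covariance as first choice (by arm if wanted), with the practice random effect and without the participant intercept.
4. Name participant intercept plus AR1, again with the practice effect, as the fallback if the first choice does not converge. Because this fallback assumes equal SDs, show the SD at each visit beside the result if it is used.

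The cost is SAP wording only. No new data or change to the sample size is needed, and six covariance parameters per arm are easily estimated from a planned 460 patients per arm.
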